8.9 Investigational product accountability

The investigator site must maintain adequate records documenting the receipt, use, loss, or other disposition of the investigational product supplies. All investigational products will be accounted for using a drug accountability form/record.

Throughout the study, detailed investigational product accountability records, including tube weights, will be maintained for each participant by study staff.

The participants and/or caregivers will be asked to bring all dispensed investigational product (including empty, partial used and unused tubes) and the treatment diary to the clinic at every visit. Detailed drug accountability records, including fortnightly tube weights measured in the site research facility, will be maintained by unblinded personnel for each participant.

The original investigational product accountability log, or equivalent document, must be accurately completed, and retained at the study site when the study is complete. The accountability log will be an unblinded document until study completion and therefore should only be accessed by unblinded site personnel.

8.10 Disposal of the study treatments

The sponsor or designee will provide guidance on the destruction of unused investigational product (eg, at the site). If destruction is authorized to take place at the investigator site, the investigator must ensure that the materials are destroyed in compliance with applicable environmental regulations, institutional policy, and all destruction must be adequately documented.

For all investigational product returned to the investigator by participants and/or the parents/legal guardians, the investigator will maintain the returned supply until destruction is authorized by the Sponsor.

Only unblinded personnel should have access to or view any returned product. The sponsor or designee will provide instructions as to the disposition of any unused investigational product.

8.11 Compliance monitoring

The IP will be weighed at every visit and the diary reviewed. Both product weights and product application information will be captured in the EDC system.

Visits 2-5 are conducted for the purposes of compliance monitoring and participant training only. The aim is for participants to undertake 5 supervised applications during the first 2 weeks of treatment (including at the end of visit 1) to monitor compliance and encourage consistent adherence to the application regimen. To minimize the burden on participants sufficient variance has been included to allow gaps of up to 7 days between supervised applications. It is anticipated that after 5 observed applications during the first 2 weeks, participants will be sufficiently trained to reliably carry out the treatment. Compliance visits are not expected to take place on weekends. Only one application per day is to be supervised. The sessions should be arranged such that participants can fully adhere to the treatment regimen, requiring 2 applications per day, once in the morning and once in the afternoon/evening separated by at least 6 hours.

Treatment usage should be determined from the IMP weights during every visit so that the information can be shared with the participant (and recorded in the treatment diary) in the context of expected usage, and any required changes in dosage or application technique suggested prior to the supervised application. Supervised applications should be performed at every study visit (after any scheduled skin assessments) to ensure consistent adherence to the dosing regimen. Re-training should be provided as required based on completion of the diary, product weights and application technique. The criteria for assessing usage is provided in the next section.

The diary should be reviewed at every visit for completeness and any gaps in application discussed with the participant. If, at all study visits except visit 1-5, the participant is found to have missed more than 20% of the scheduled applications, and/or missed more than 4 consecutive applications, and/or missed either of the 2 applications immediately preceding a study visit involving skin assessments the participant should be withdrawn. During Visits 1-5 the study Investigators may use their discretion to judge a participant's ability to adhere to the treatment regimen.

8.12 Treatment dosing and compliance

Dosing is by finger-tip unit (FTU) rather than by gram. The dose for both investigational products in this study is 1 FTU applied to the volar face of one forearm each twice per day (Figure 8.1).

Despite the different size tubes for crisaborole ointment and betamethasone valerate cream, both have a nozzle size of approximately 7mm (38.48cm²) ensuring consistent dosing between them.

This means the anticipated weight per FTU of each product is approximately 1.0g (based on established dosing of 0.5g from a 5mm nozzle, having a 19.63cm² area).

The treatment area on the volar face of the forearm from the elbow crease down to the wrist is the equivalent of 2 hands or 264 cm² (1.46% body surface area), making the dosage 3.8 (1.9-7.6) mg/cm².

With 2 applications per day, the expected usage is 2g per day of each product. Over the 28-day treatment regimen total usage of each product is estimated at 56g.

Due to the expected variability of the FTU participants are expected to apply between 28 and 112g of each product (assessed at the end of treatment) to be compliant with the protocol.

The per gram dosing is consistent with the manufacturer's recommendations for crisaborole ointment (and with international marketing authorizations). Retraining should be provided at each visit where IMP usage falls outside the expected parameters provided here.

[figure not shown]

Figure 8.1: A guide to dosing topical creams

Rather than excluding participants based on the amounts of treatment used, the focus should be on education so that participants can achieve satisfactory compliance by the end of the study. At Visit 5 SMART Study 1 Protocol V5.0 27Jan21.docx, IRAS 269415

Page 82 of 106

This document is confidential – No part of it may be transmitted, reproduced, or used by other persons without prior written authorisation from The University Of Sheffield.

the study Investigators may use their discretion to judge a participant's ability to meet the target usage based upon their application technique, the adherence to the application schedule and the amounts used together. Participants deemed at Visit 5 to be incapable of meeting the usage requirements by the end of the study should be withdrawn.

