7.4.6 Visit 6, Day 15 +/- 3 days (approx. 2.5 hours)

- Re-confirm verbal ascent to continue the study
- Capture adverse events and new concomitant medications
- Check that an appropriate method of contraception is in use
- Check compliance with dosing conditions
- Transfer participant to skin barrier suite
- Participants will need to acclimatize the skin on their forearms to the room conditions for 20 minutes.
- The measurement sites should be marked out on each arm using a marker pen (as discreetly as possible). The marker is easily removed by washing the skin at the end of the study visit. Hair interferes with the measurements, so where present we may need to trim it.
- Once acclimatised the condition of the skin should be assessed:
 - Visually score skin dryness and redness/erythema at each treatment area
 - Capture 2D skin images of the test areas of skin
 - Perform Mexameter measurements of objective skin redness at each site
 - Take OCT (structural & angiographic) images/scans with the Vivosight at each test site
 - Measure TEWL at each test site
 - Collect FTIR spectra at each test site
- Transfer patients back to the site research facility (if different)
- Weigh IMP's, record weights in the CRF and treatment diary, and inform participants of their usage in the context of expected usage.
- Check all diary entries for missing applications and adverse events (skin reactions reported at the time of application).
- Ask the participant to perform a supervised product application (after measurements).
- Provide re-training/guidance to improve on application technique and/or dosing 'as required'
- Arrange taxi transfer for next session

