7.5 Randomization & blinding

The participant will be assigned a randomization number (Trial Number) at Visit 1. This will be the next available number on the Randomization list. This number will be the principle identifier against which the study data will be stored. Allocation of the randomization number is considered the point of entry onto the trial, which should be recorded on the Participant Screening, Enrollment & Completion Log.

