7.10.2 Participant withdrawal

When an individual who has signed the Informed Consent Form is not enrolled in the study or withdraws/is withdrawn prior to completing the study, the reason is to be documented on the Participant Screening, Enrolment & Completion Log. Reasons for participant withdrawal may include:

1. Participant is determined to be ineligible after enrolment
2. Participant's choice to withdraw
3. Exclusion criteria met
4. Non-compliance with the study protocol.
5. Adverse event, including a relapse of AD (defined as an escalation in treatment, i.e. the need for topical corticosteroids).
6. Loss-to-follow (participant cannot be contacted)
7. Other

Participants may withdraw from the study at any time at their request, or they may be withdrawn at any time at the discretion of the PI, or designee for safety, behavioural, or administrative reasons. If a participant does not return for a scheduled visit, at least 2 attempts will be made to contact the participant in order to establish the reason for withdrawal, and the outcome will be documented, if reasonably possible within the constraints of the study design. No more than 4 attempts will be made to contact participants; a voicemail to a personal mobile number may be left once but this will not detail any study or clinical information, it will be limited to a request to call back on a given number. The PI or designee should inquire about the reason for withdrawal, request that the participant return

for a final visit, if applicable (if withdrawing from the study during the treatment period between study visits), and follow-up with the participant regarding any unresolved adverse events. In such circumstances, where the treatment regimen has not completed the final visit will be conducted solely to retrieve the products and capture any unreported AE's.

Additional participants may be enrolled in the study, up to the maximum recruitment target, to compensate for early participant withdrawal.

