8.13 Investigator termination of participant involvement

Examples of participant non-compliance that may arise are:

- The participant fails to satisfactorily follow the study schedule (appointments not attended within the given timeframes), as per the schedule of events and this affects collection of data pertaining to the primary outcome measures.
- The participant fails to apply the product at the specified times/days. Participants who miss more than 20% of the scheduled applications, and/or miss more than 4 consecutive applications, and/or miss either of the 2 applications immediately preceding a study appointment should be withdrawn.
- The participant fails to use the investigational products in acceptable quantities (see "treatment dosing and compliance"). At each session usage should be assessed. Where IP use is above or below expectations a new demonstration should be provided. Supervised applications are performed at every visit as required.
- The participant fails to bring the diary to any visit and cannot provide their usage history. Where a diary is not available, the participant should be asked to recite their application history for the given study period and bring the diary at the next visit. Every effort should be

made to retrieve the diaries. Where completed diaries cannot be obtained *AND* a participant's application history cannot be documented the participant should be withdrawn.

- The participant fails to bring the IP to study visits. If the participant fails to bring the IP to any visit they should be asked to return as soon as possible with the IP for weighing. A weight post 4-weeks treatment is required for compliance purposes (it is desirable for all other visits).
- Participants who inadvertently use the IP in the morning before the study visit – In these cases a new appointment should be scheduled where possible – if this is not possible within the constraints of the study the participant should be withdrawn.

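### Compliance withdrawals up to Visit 6a remove the Day 29 scan, so the estimate labelled ITT/FAS is conditional on passing those checks, and the last-two-applications rule loses some of this data avoidably

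*Protocol*

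**What the plan says.** **Population.** Protocol 7.5 places entry at Visit 1: "Allocation of the randomization number is considered the point of entry onto the trial". Protocol 10.3 defines the ITT population as those who consented and were issued treatment, and keeps it as primary. SAP 5 defines the FAS as all randomised and leaves the per-protocol (PPS) analysis optional. SAP 7.6 does not replace missing data.

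**Scans.** Structural OCT is taken on Days 1, 15, 29 and 57 (Protocol 4.7). Visits 2-5 are for compliance and training, and Visit 6a repeats their procedures (7.4.7), so none of these has OCT.

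**Withdrawal for compliance.**
- 8.12 expects 28-112 g of each product by the end of treatment. It starts with "Rather than excluding participants based on the amounts of treatment used, the focus should be on education" but then says "Participants deemed at Visit 5 to be incapable of meeting the usage requirements by the end of the study should be withdrawn".
- 8.11 applies from Visit 6. It withdraws for more than 20% missed, for more than 4 consecutive missed, or on its last limb: "missed either of the 2 applications immediately preceding a study visit involving skin assessments the participant should be withdrawn".
- 8.13 repeats the rule for participants who "miss either of the 2 applications immediately preceding a study appointment should be withdrawn". It also withdraws where diaries are unavailable and "a participant's application history cannot be documented the participant should be withdrawn".

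**After withdrawal.** For people leaving between visits, 7.10.2 says that "where the treatment regimen has not completed the final visit will be conducted solely to retrieve the products" and capture adverse events. No OCT visit is scheduled for anyone after withdrawal.

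**Order of procedures.** At Visit 6 (7.4.6) the step "Check all diary entries for missing applications and adverse events" is listed after the scans. Visit 7 has the same order.

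**The concern.** The protocol treats stopping treatment and leaving the study as one event. A participant who fails a compliance check before Day 29 stays in the declared analysis population but has no primary outcome. The Day 29 estimate will be labelled as covering everyone randomised, while the data behind it are filtered on adherence after randomisation. The optional PPS analysis cannot show whether this matters, because it is a subset of the FAS and those removed have no Day 29 scan.

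Part of the loss looks needless. Missing one of the last two applications before Visit 6 can end participation for someone well inside the general 20% limit. Under 8.13 the same can happen before Visit 6a, where no skin is measured. The trial plans 37 participants for 33 completers, so a few avoidable losses count.

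**Working it through.** **1. The plan's own figures.** Inputs from Protocol 10.1: changes of -4.44 and -0.88 µm (difference 3.56), SD 5, 80% power; two-sided 5% from SAP 7.5. A two-sample t-test needs 32 per group, and 33 per group gives 81%. With 10% dropout, 33/0.9 = 36.7, so 37. Both stated figures reproduce, leaving room for 4 losses from any cause.

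**2. OCT available by route.**

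| Breach acted on at | Day 15 | Day 29 |
|---|---|---|
| Visit 5 (day 5, window to day 12) | none | none |
| Visit 6, diary check after scan | kept | none |
| Visit 6a | kept | none |
| Visit 7, diary check after scan | kept | kept |
| Visit 7, morning use that cannot be rescheduled | kept | none |

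**3. Effect in the primary model.** SAP 7.1 models change from day 1, so a participant with baseline only contributes nothing. A Day 15-only pair barely helps either. With subject as the only random effect, the subject term cancels from the difference between forearms, so the Day 15 difference carries no information about the Day 29 difference. Taking a correlation of 0.25 (assumed; residual variance 18.75), the Day 29 standard error is √(2 × 18.75/33) = 1.066 with 33 complete pairs. It is still 1.066 after adding 4 Day 15-only pairs, and √(2 × 18.75/37) = 1.007 with all 37 complete. A covariance term for arm within subject would recover part.

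**4. Size of the last-two rule at Visit 6.** Two applications a day for 14 days is 28, so one miss is 1/28 = 3.6%. The 20% limit is 5.6 applications, so it takes 6 misses to breach it. No miss rate is given. Assume each application is missed independently with probability p:
- Any trigger: 1 − (1−p)².
- Triggered but within the 20% limit: 2p(1−p)·P[Bin(26,p) ≤ 4] + p²·P[Bin(26,p) ≤ 3].
- The triggering application is the only miss: 2p(1−p)²⁷.
- Any trigger at Visit 6 or 6a under the 8.13 wording: 1 − (1−p)⁴.

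| Expected number of 37 | p = 1% | 2% | 5% | 10% |
|---|---|---|---|---|
| Any trigger, Visit 6 | 0.7 | 1.5 | 3.6 | 7.0 |
| Of these, within 20% limit | 0.7 | 1.5 | 3.6 | 6.2 |
| Of these, only miss | 0.6 | 0.9 | 0.9 | 0.4 |
| Any trigger, Visit 6 or 6a | 1.5 | 2.9 | 6.9 | 12.7 |

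The only-miss probability peaks at p = 1/28, at 2.7%, which is 0.027 × 37 ≈ 1 participant. At p = 5% the 20% rule fires by Visit 6 in 0.2%.

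**5. Clustered misses.** Keep the mean at 5% but let 90% of people miss 1% and 10% miss 41% (0.9 × 1% + 0.1 × 41% = 5%). The 20% rule then fires in 9.9% and the last-two rule in 8.3%. The last-two rule catches someone inside the 20% limit in only 1.8%, or 0.018 × 37 = 0.7 participants, against 3.6 under independence.

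**6. Size of the selection.** Suppose 4 of 37 are removed. If their true contrast were zero, the retained-only estimate exceeds the all-randomised one by 37/33 − 1 = 12.1%; at half contrast, by 37/35 − 1 = 5.7%. Someone retrained after a missed application should sit near full contrast, so keeping them changes the estimate little and adds a pair.

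**7. Following Visit 5 stops off treatment.** They would be 29 − 12 = 17 to 29 − 5 = 24 days off drug at Day 29, and Protocol 2.8.1 says thinning reverses within weeks, so assume no contrast. With 4 of 37, the mean falls to 3.56 × 33/37 = 3.18 µm. Paired power uses an SD of the difference of 5√(2(1−ρ)), with ρ an assumed correlation. By simulation it is 75% against 80% for 33 pairs at ρ = 0, and 86% against 90% at ρ = 0.25.

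**The case against.** The strongest reply is that this is a mechanistic comparison of two regimens taken twice daily for 28 days, so an on-regimen contrast is what is wanted. The protocol puts education before exclusion, supervises five applications in the first two weeks, sends reminders, allows 10% dropout and permits replacement up to the recruitment cap. Disposition, deviation and discontinuation outputs are planned, so losses will be visible. Scanning arms weeks off drug would dilute the primary contrast.

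Much of this stands. The off-treatment point is a real trade-off, so that follow-up is not part of the main request. The on-regimen aim is legitimate too, but it supports a defined PPS analysis, not an adherence filter inside an estimate called ITT.

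Four stronger readings are tempting and not supported:
- *The estimate covers only compliant people.* Diary breaches first found at Visit 7 come after the scan and stay in, and use outside 28-112 g at the end is not a stated exclusion from the FAS.
- *The arms become unbalanced.* Both forearms leave together.
- *Several participants would be lost over a single missed application.* Most of those caught at the higher assumed rates have missed others as well.
- *7.10.2 itself forbids OCT after a Visit 5 withdrawal.* That clause concerns people leaving between visits. The scan is absent because no outcome visit follows withdrawal.

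**Conclusion.** The point holds in a limited form. The Day 29 estimate is conditional on not being withdrawn for compliance at Visits 5 to 6a, which the ITT/FAS label does not say. The last-two rule also discards primary data from people within the protocol's own general limits, and 8.13 conflicts with 8.11 by reaching Visit 6a.

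At Visit 6 the avoidable loss is about 0.7 to 6.2 of 37 for assumed independent miss rates of 1 to 10%. It is smaller if misses cluster: 0.7 instead of 3.6 at a 5% mean in the example above. These are illustrations, since the documents give neither a miss rate nor a number of compliance withdrawals. The comparison between forearms remains valid among those scanned. What is affected is whom the estimate describes, and precision. The narrow changes are worth making because they use visits already scheduled.

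**What to change.** 1. **Protocol 8.13:** limit the last-two rule to visits with skin assessments, as 8.11 does, so that Visit 6a is no longer a trigger.
2. **Protocol 8.11 and 8.13:** where a participant is within the 20% and 4-consecutive limits but missed either of the last two applications before Visit 6, replace withdrawal with: log the deviation, retrain, continue treatment and attend the scheduled Day 29 OCT. Leave the more-than-20%, more-than-4-consecutive and Visit 7 residue rules as they are.
3. **SAP 5:** include all available OCT in the FAS and make the PPS analysis of the primary endpoint mandatory. Exclude from the PPS anyone with more than 20% or more than 4 consecutive applications missed, either of the two applications before the Day 29 scan missed, or use outside 28-112 g.
4. **Reporting:** describe the Day 29 FAS estimate as conditional on not being withdrawn for compliance at Visits 5 to 6a.

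Off-treatment OCT for participants stopped at Visit 5 is optional, given the power cost shown in step 7.

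Cost: a short amendment to two protocol sections, a few lines in the SAP, one extra planned analysis, and slight dilution from a few missed doses. Items 1 to 4 add no visits to the schedule.

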8.12.1 IMP application during the morning of study visits

Treatments should not be applied on the day of study visits where a supervised application is scheduled OR where skin assessments are scheduled (as per Table 7.1).

To remind participants not to apply the morning application reminders should be issued. Where possible this should be done by text message using a work mobile phone. Where this is not possible telephone or emails reminders can be sent according to the preference of the participant.

Where the treatments have been applied on the day of study visits 6 and 7, the visit will need to be re-scheduled, because treatment residues will interfere with the assessments. Washing the skin is not an acceptable substitute. Treatments should not be applied on the day of study visits 6 and 7 until after skin assessments have been conducted.

Where the treatments have been applied on days not involving skin assessments, and 6 hours has passed since the last application the visit can be conducted as normal AND the application recorded as the second daily application (no further application that day). Where 6 hours has not passed, the supervised application should not be performed to prevent overdosing. The deviation from the protocol should be logged on the protocol deviation form. In this situation the session will not require rescheduling and all other activities should be completed as normal.

On issuing the treatment diary, the relevant mornings should be highlighted to remind participants not to apply the product as described above.

